6.4.9. Time Period and Frequency of Detecting AEs and SAEs

The investigator or site staff is responsible for detecting, documenting and reporting events that meet the definition of an AE or SAE.

SAEs and AEs of special interest will be collected throughout all parts of the study, beginning at the time of first dose of IP through the Week 24 visit. In addition, any SAEs assessed **as related** to study participation (e.g., study treatment, protocol-mandated procedures, invasive tests, or change in existing therapy), or **related** to a GSK concomitant medication, will be recorded from the time a subject consents to participate in the study up to and including any follow up contact at Week 24. All SAEs will be reported to GSK within 24 hours, as indicated in [6.4.11](#).

Non-serious AEs will be collected from the time of the first dose of IP until the Week 12 Visit, in Part A and Part B1 ([Table 1](#)). Non-serious AEs will not be collected in Part B2 if the IDMC recommends a focused safety data collection after reviewing the safety data from subjects in Parts A and B1. However, AEs of special interest (Section [6.4.6](#)) and AEs leading to permanent discontinuation of IP will be continue to be collected in Part B2 ([Table 1](#)).

For purpose of clarity, it is reiterated that events that are to be reported as potential study endpoints will be reported in all subjects up to and including the Week 24 Visit. It is expected that investigators will enter potential endpoints events into the subject's eCRF within 24 hours of becoming aware of the event.

6.4.10. Method of Detecting AEs and SAEs

Care must be taken not to introduce bias when detecting AEs and/or SAEs. Open-ended and non-leading verbal questioning of the subject is the preferred method to inquire about AE occurrence. Appropriate questions include:

“How are you feeling?”

“Have you had any (other) medical problems since your last visit/contact?”

“Have you taken any new medicines, other than those provided in this study, since your last visit/contact?”

6.4.11. Prompt Reporting of Serious Adverse Events and Other Events to GSK

SAEs, pregnancies, and liver function abnormalities meeting pre-defined criteria will be reported promptly by the investigator to GSK as described in the following table once the investigator determines that the event meets the protocol definition for that event.

SAEs, non-serious AEs related to study treatment, pregnancies, medical device incidents, and liver function abnormalities meeting pre-defined criteria will be reported promptly by the investigator to GSK as described in the following table once the investigator determines that the event meets the protocol definition for that event.

Type of Event	Initial Reports		Follow-up Information on a Previous Report	
	Time Frame	Documents	Time Frame	Documents
All SAEs	24 hours	"SAE" data collection tool	24 hours	Updated "SAE" data collection tool
Pregnancy	2 weeks	"Pregnancy Notification Form"	2 weeks	"Pregnancy Follow-up Form"
Non-serious adverse events related to study treatment	5 calendar days	"Adverse Reaction" data collection tool	2 weeks	Updated "Adverse Reaction" data collection tool
Liver chemistry abnormalities				
ALT \geq 3xULN and Bilirubin \geq 2xULN (>35% direct) (or ALT \geq 3xULN and INR>1.5, if INR measured) ¹	24 hours ²	"SAE" data collection tool. "Liver Event CRF" and "Liver Imaging" and/or "Liver Biopsy" CRFs, if applicable ³	24 hours	Updated "SAE" data collection tool/"Liver Event" Documents ³
ALT \geq 8xULN; ALT \geq 3xULN with hepatitis or rash or \geq 3xULN and <5xULN that persists \geq 4 weeks	24 hours ²	"Liver Event" Documents (defined above) ³	24 hours	Updated "Liver Event" Documents ³
ALT \geq 5xULN plus bilirubin <2xULN	24 hours ²	"Liver Event" Documents (defined above) do not need completing unless elevations persist for 2 weeks or subject cannot be monitored weekly for 2 weeks ³	24 hours	Updated "Liver Event" Documents, if applicable ³
ALT \geq 5xULN and bilirubin <2xULN that persists \geq 2 weeks	24 hours ²	"Liver Event" Documents (defined above) ³	24 hours	Updated "Liver Event" Documents ³
ALT \geq 3xULN and <5x ULN and bilirubin <2xULN	24 hours ²	"Liver Event" Documents (defined above) do not need completing unless elevations persist for 4 weeks or subject cannot be monitored weekly for 4 weeks ³	24 hours	Updated "Liver Event" Documents, if applicable ³

1. INR measurement is not required; if measured, the threshold value stated will not apply to subjects receiving anticoagulants.

2. GSK/TIMI Hotline must be contacted at onset of liver chemistry elevations to discuss subject safety
3. Liver Event Documents (i.e., "Liver Event CRF" and "Liver Imaging CRF" and/or "Liver Biopsy CRF", as applicable) should be completed as soon as possible.

Liver chemistry stopping criteria and follow-up criteria are defined in [Appendix 3](#).

The method of detecting, recording, evaluating and follow-up of AEs and SAEs plus procedures for completing and transmitting SAE reports to GSK are provided in the SPM. Procedures for post-study AEs/SAEs are provided in the SPM.

6.4.11.1. Regulatory Reporting Requirements for SAEs

Prompt notification of SAEs by the investigator to GSK is essential so that legal obligations and ethical responsibilities towards the safety of subjects are met.

GSK has a legal responsibility to notify both the local regulatory authority and other regulatory agencies about the safety of a product under clinical investigation. GSK will comply with country specific regulatory requirements relating to safety reporting to the regulatory authority, Institutional Review Board (IRB)/Independent Ethics Committee (IEC) and investigators.

Investigator safety reports are prepared for suspected unexpected serious adverse reactions according to local regulatory requirements and GSK policy and are forwarded to investigators as necessary. These reports to investigators will remain blinded with respect to treatment allocation.

An investigator who receives an investigator safety report describing a SAE(s) or other specific safety information (e.g., summary or listing of SAEs) from GSK will file it with the IB and will notify the IRB/IEC, if appropriate according to local requirements.

6.4.12. 12-lead ECG

Full 12-lead ECGs will be recorded at the time points specified in [Table 1](#). All 12-lead ECGs will be read locally by the Investigator or his/her designate. Documentation of the ECG (ECG tracing and investigator interpretation) will be maintained in the subject's source document record.

Those subjects with a baseline QTc interval >450 msec will undergo the following:

- Actively assess and treat potential causes of QT prolongation (e.g. electrolyte disturbance, acute ischemia, and contributing medications) in accordance with clinical care.
- Perform continuous ECG monitoring (i.e. telemetry monitoring) for at least 48 hours while hospitalized with ACS. If the subject is discharged prior to 48 hours of telemetry, a 12 lead ECG will be obtained prior to discharge to assess the QTc.
- Obtain a daily 12 lead ECG while hospitalized.
- Obtain pre-discharge ECG 2-4 hours after dosing of IP to evaluate QTc.

Clinically significant QTc prolongation, not attributed to other reversible factors, should be discussed with TIMI hotline/medical monitor.

6.4.13. Physical Examination

Brief physical examination: at minimum, assess weight (enrollment only), height (enrollment only), and perform a focused pulmonary and cardiovascular exam. During hospitalization for the qualifying event, it is acceptable to obtain weight and height at any time prior to hospital discharge.

If possible, the same person should perform the physical exam for an individual subject at each visit for that subject.

6.4.14. Vital Signs

Vital sign measurements will include systolic and diastolic blood pressure and resting heart rate. Measurements taken at the hospital prior to randomization will be recorded as the baseline results. Sitting vital signs are taken at each clinic visit prior to obtaining blood samples according to AHA guidelines [Pickering, 2005]. If possible, all measurements should use the same cuff size and same equipment at each visit. (Refer to SPM for more detailed guidelines on taking blood pressure and heart rate measurement).

6.4.15. Laboratory Assessments

All protocol required laboratory assessments, as defined in [Table 1](#) and [Table 2](#), must be performed by the central laboratory, unless specified otherwise. Laboratory assessments must be conducted in accordance with the Central Laboratory Manual and Protocol Time and Events Schedule. Laboratory requisition forms must be completed and samples must be clearly labelled with the subject number, protocol number, site/center number, and visit date. Details for the preparation and shipment of samples will be provided by the Central Laboratory. Reference ranges for all safety parameters will be provided to the site by the Central Laboratory.

If additional non-protocol specified laboratory assessments are performed at the institution's local laboratory and result in a change in subject management or are considered clinically significant by the investigator (e.g., SAE or AE or dose modification) the results must be recorded in the subject's eCRF.

All study-required laboratory assessments will be performed by a central laboratory, apart from laboratory tests done at screening to determine subject eligibility (e.g., liver chemistry and renal function tests) (see Section [3.1.3](#)) and to evaluate potential cardiac ischemic events during participation (e.g., cardiac troponin, see Section [6.2](#)). All cardiac biomarker (troponin and/or CKMB) results, where clinically relevant, done by the local laboratory must be entered into the subject's eCRF.

At the Baseline Visit, blood will be collected for HBsAg and hepatitis C antibody and sent to the central laboratory for analysis. If either test is positive, refer to Section [6.4.2](#).

Blood samples for safety clinical laboratory tests will be collected at the times specified in [Table 1](#) for analysis at the central laboratory, to include:

- *Hematology*: hematocrit, hemoglobin, platelet count, white blood cell count, neutrophil count.
- *Clinical chemistry*: alkaline phosphatase, alanine aminotransferase (ALT), aspartate aminotransferase (AST), total bilirubin, total protein, serum albumin, blood urea nitrogen, calcium, chloride, serum creatinine, eGFR,¹ potassium, sodium, bicarbonate, plasma glucose, hs-CRP.
- *Lipids*: total cholesterol, high density lipoprotein cholesterol (HDLc), LDLc, triglycerides.
- *Other*: in subjects with type 1 or 2 diabetes mellitus - HbA1c.
For lipids, plasma glucose, and HbA1c: The subjects should fast whenever possible for ≥ 8 hours prior to obtaining the blood sample. For pre-randomization blood samples, obtain the sample even if the subject has not fasted for at least 8 hours.
- *CV Biomarkers*: discussed in detail in Section 6.6, Appendix 5 .

In addition, in the Renal and Expanded Laboratory Substudy (Part A), blood samples will be obtained in a subset of subjects to assess clinical chemistry, as well as other cardiovascular biomarkers, more frequently (Table 2). The target enrollment for this substudy is 600 subjects who complete at least the in-hospital period of laboratories. Enrollment in the substudy will be monitored such that approximately equal proportions of STEMI, and NSTEMI will be recruited.

For females of child-bearing potential, pregnancy testing will be performed at the time points specified in Table 1. A urine β -hCG pregnancy test will be done or serum β -hCG will be assessed according to Table 1. At the time points when a clinic visit is not scheduled, the subject should perform the pregnancy test using an at-home urine pregnancy test kit. The results of the at home pregnancy test at Week 8 can be captured at the next in clinic visit. Any positive test at home should be reported immediately to the site. A positive urine pregnancy test may be confirmed by sending a serum sample to the central laboratory for analysis of β -hCG.

6.5. Health Outcomes: EQ-5D

The EuroQOL five dimension questionnaire (EQ-5D; EuroQol Group) is a standardized instrument for use as a measure of health outcome that provides a simple descriptive profile and a single index value for health status. The EQ-5D self-report questionnaire consists of two parts comprising the EQ-5D descriptive system and the EQ visual analogue scale (VAS). Complete instructions for completion are provided in the SPM.

The EQ-5D descriptive system comprises five dimensions of health (mobility, self-care, usual activities, pain/discomfort and anxiety/depression). Each dimension comprises five levels (no problems, slight problems, moderate problems, severe problems, and extreme

¹ Based on serum creatinine and the Chronic Kidney Disease Epidemiology Collaboration (CKD-EPI) equation.

problems) and is referred to as the EQ-5D-5L. A unique EQ-5D-5L health state index value is defined by combining one level from each of the five dimensions.

The EQ VAS records the respondent's self-rated health status on a vertical graduated visual analogue scale (0=worst imaginable – 100=best imaginable). This questionnaire is to be administered in select countries based on local Health Technology Assessment requirements, and will supplement cost effectiveness analyses.

Health status will be assessed for subjects participating in a select number of countries in Part B1 and B2 at the times specified in [Table 1](#) (Part B1: at discharge, Week 12, and Week 24, end of study; Part B2: at discharge and Week 12 only). The paper questionnaire will be completed by the subject at the designated clinic visits and it will not be completed at the Week 24 phone visit in Part B2.

For analysis purposes, EQ-5D-5L data will be pooled from Part B1 and B2 for the discharge and Week 12 visits. A separate subanalysis will be performed for those subjects in Part B1 for whom three data points are available, to assess if the health status data persists at Week 24.

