2.4. Exploratory Objectives

Exploratory objectives are to evaluate the pharmacokinetics (PK) and PK/pharmacodynamics (PD) of losmapimod, and the effect of losmapimod on health status in subsets of subjects according to the Time and Events tables. Other (non-coronary) atherothrombotic vascular events will also be captured as an exploratory endpoint. Evaluation of genomics and cardiovascular and inflammatory biomarkers are described in [Appendix 4](#) and [Appendix 5](#), respectively.

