3.1. Study Design

[figure not shown]
This is a randomized, placebo-controlled, double-blind, parallel-group, multicenter study which will be conducted in two parts ([Figure 1](#)). The trial will include approximately 25,500 subjects presenting with NSTEMI or STEMI. Subjects will be randomized 1:1 to receive either oral losmapimod 7.5mg BID or matching placebo BID for 12 weeks in addition to standard of care, and will be followed for an additional 12 weeks after completing treatment, for a total study duration of 24 weeks.

An Independent Data Monitoring Committee (IDMC) will have study oversight to ensure scientific integrity of the data and subject safety, and an independent CEC blinded to treatment will adjudicate outcome events.

This study has two parts (Part A and Part B).

- Part A: leading cohort of 3,500 subjects will be randomized to provide an initial assessment of safety and exploratory efficacy (~200 adjudicated + pending primary endpoint events) before progressing to Part B. Efficacy data from this stage of the study will not be used in the primary efficacy analysis of the trial.
- Part B: the main cohort will be event driven with approximately 22,000 subjects randomized to provide the main assessment of efficacy with an event target of 1,400 adjudicated primary endpoint events, and 1,000–1,200 adjudicated CV death and MI events.

Figure 1 Two Part Study Design

Composite of adjudicated MACE (major adverse cardiovascular events) defined as cardiovascular death, myocardial infarction, or severe recurrent ischemia requiring urgent coronary artery revascularization.

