6.3.2. Secondary Efficacy Endpoints

Principal Secondary Endpoint: The principal secondary endpoint is the time to first occurrence of the composite of adjudicated CV death or MI.

Additional Secondary Endpoints:

- The composite of CV death, MI, or hospitalization for HF.
- The expanded composite of arterial CV events, defined as CV death, MI, SRI-UR, or stroke.
- The composite of coronary events (defined as CHD death, MI, SRI-UR, or any unplanned coronary artery revascularization).

Planned coronary artery revascularizations are those initial or staged interventions performed based on the initial qualifying ACS.

- The composite of CV death or hospitalization for HF
- The composite of CV death, MI or stroke.

- The composite of CV death, MI, SRI-UR, stroke or hospitalisation for HF
- The primary and principal secondary endpoints will be evaluated replacing CV death separately with CHD death (“Coronary MACE”) and all-cause death.
- The primary and principal secondary endpoints will be evaluated replacing all MI with Type 1 (spontaneous) MI.
- Individual components of the composite endpoints (including all-cause mortality).
- Definite or probable stent thrombosis.
- Any re-hospitalization within 30 days of discharge.

For the primary and each of the secondary endpoints, the principal analysis will be through 12 weeks, with additional analyses through 4 and 24 weeks unless otherwise stated. In addition, a recurrent event analysis (i.e., accounting for subjects who experience multiple events) will be conducted for each composite endpoint. Additional endpoints will be specified in the RAP.

All endpoints are defined in detail in the CEC Charter.

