The principal secondary endpoint of CV death/MI will be tested provided the primary endpoint is statistically significant at the 5% level. For the principal secondary endpoint of CV Death or MI: a minimum of 1,000 adjudicated events will provide approximately 90% power to detect an 18.5% reduction in risk (hazard ratio=0.815) and close to 80% power to detect a 15% reduction in risk at a 5% significance level. At the 5% significance level, the minimum detectable effect (i.e., the smallest effect to give a significant p-value) is approximately 12%.

The anticipated placebo MACE event rate (~7%) is estimated from the ticagrelor treatment group of the PLATO study using the individual Kaplan-Meier cumulative event rate estimate from the NSTEMI (7.1%) and STEMI (6.0%), taking into account a 20% reduction in events as a consequence of the recent changes to the universal definition of MI and the use of SRI-UR as a replacement for stroke.

The aggregate event-rate data will be periodically reviewed by the Executive Committee and sponsor. Should emerging data diverge significantly from protocol assumptions the total sample size to achieve the event target for Part B may be adjusted if deemed appropriate.

Recruitment may be closed prior to 1400 events if the sample size for part B is anticipated to exceed 24,000 subjects.

Assessment of Safety in Parts A & B1

All 25,500 subjects estimated to enroll in the trial would contribute to a robust overall safety database of clinical adverse events, including liver events.

In addition, the totality of available safety data from Part A (N=3,500) will be evaluated prior to starting Part B, and an additional formal evaluation of safety will be conducted by the IDMC once Part B has enrolled approximately 3,500 subjects (completion of Part B1), to support a combined analysis of 7,000 subjects' safety data. After this point, if considered appropriate by the IDMC, the time and events schedule for data collection will be revised (Section 6). As noted, such decisions will be made based on the totality of

the data, but for illustrative purposes, power and detectable effect with respect to aspects of safety analysis has been considered.

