8.3.5.3. Health Outcomes Analyses

Health economic outcomes will be assessed in this study including medical resource utilization and health status assessment, which will both be used to assess the cost-effectiveness of losmapimod in the ACS population. With the exception of EQ-5D-5L, the events of interest will be measured at discharge, Week 4, Week 12, and Week 24 (end of study) with possibility for an extension registry. The EQ-5D-5L will be collected in a select number of countries in Part B1 at discharge, Week 12, and Week 24 (end of study), while it will be collected in those same countries in Part B2 at discharge and Week 12 only. The paper questionnaire will be completed by the subject at the designated clinic visits and it will not be completed at the Week 24 phone visit in Part B2.

The health economic evaluations, to be detailed in a separate Economic Statistical Analysis Plan, will include: total treatment costs; cost per vascular event avoided; cost per life years saved (LYS); and cost per quality-adjusted life years (QALY) gained.

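### The exploratory Week 24 EQ-5D-5L subanalysis keeps only Part B1 subjects with all three forms, so it conditions on survival and attendance and tends to overstate persistence

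*Protocol*

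**What the plan says.** Protocol section 6.5 sets the EQ-5D-5L schedule as "Part B1: at discharge, Week 12, and Week 24, end of study; Part B2: at discharge and Week 12 only". For analysis, "EQ-5D-5L data will be pooled from Part B1 and B2 for the discharge and Week 12 visits". Week 24 is handled apart from this pooled analysis, in a subanalysis of Part B1 subjects "for whom three data points are available, to assess if the health status data persists at Week 24". No other Week 24 analysis of the instrument is described.

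On collection, section 8.3.5.3 says "The paper questionnaire will be completed by the subject at the designated clinic visits", and section 6.5 says the same. Sections 3.1.4 and 4.5 provide that subjects who stop investigational product early and cannot attend are followed by telephone or other means.

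The objective is exploratory. Section 2.4 describes it as evaluating "the effect of losmapimod on health status in subsets of subjects according to the Time and Events tables", and section 6.5 limits the questionnaire to selected countries.

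**The concern.** To be in the three-form set, a subject must be alive at Week 24, attend the clinic at Weeks 12 and 24, and complete a form at each of three time points. All of this happens after randomization. Death is part of the course of this disease, CV death is a component of the primary endpoint, and losmapimod is intended to reduce it (section 1.2.1). Membership of the set may therefore depend on treatment.

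Two consequences follow.

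- **Persistence.** The question is whether health status holds up at Week 24. Those whose health failed most completely are removed before it is asked. If death counts as loss of health, the answer is tilted towards persistence.
- **Arm comparison.** Any contrast of losmapimod with placebo inside the subset compares groups selected after randomization, so the 1:1 allocation no longer protects it.

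The rule also wastes data. A survivor with Week 12 and Week 24 forms but no discharge form contributes nothing, although that subject's data bear directly on the question.

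**Working it through.** The protocol states no sample size, mortality rate, utility or effect size for this subanalysis, so there is no figure of its own to reproduce. The arithmetic below only illustrates the order of magnitude.

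**From the protocol**
- Part B1 has about 3,500 subjects (section 8.2.1). This is an upper bound, since only selected countries use the questionnaire.
- Allocation is 1:1 (section 3.1).

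**Assumed, not in the protocol**
- Mean index in survivors, u: 0.75 to 0.85.
- All-cause mortality from randomization to Week 24, d: 1% to 5%. If all of Part B1 took part, this is 3,500 × 0.01 = 35 to 3,500 × 0.05 = 175 deaths.
- Share of subjects dying between Week 12 and Week 24, e: 0.3% to 2%.
- Mortality ratio, losmapimod to placebo: 0.8 or 1.25.

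**Step 1. Level at Week 24.** With death scored 0 the mean is u × (1 − d). The mean in survivors is u. The excess is u × d.
- Low end: 0.75 × 0.01 = 0.0075
- High end: 0.85 × 0.05 = 0.0425

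**Step 2. Persistence from Week 12 to Week 24.** Suppose scores in survivors are flat. The three-form set then shows a change of 0. With death scored 0 the change is −u × e.
- Low end: −0.75 × 0.003 = −0.002
- High end: −0.85 × 0.02 = −0.017

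This is the quantity that matches the stated question. The level in Step 1 counts every death since randomization and is a different quantity.

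**Step 3. Arm difference, equal index in survivors.** The three-form set shows 0. With death scored 0 the difference is u × d × (1 − ratio), where d is placebo mortality.

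| Mortality ratio | Low end | High end |
|---|---|---|
| 0.8 | 0.75 × 0.01 × 0.2 = +0.0015 | 0.85 × 0.05 × 0.2 = +0.0085 |
| 1.25 | 0.75 × 0.01 × (−0.25) = −0.0019 | 0.85 × 0.05 × (−0.25) = −0.0106 |

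**Step 4. Arm difference when the additional survivors are frailer.** Take placebo mortality 5%, ratio 0.8 (losmapimod mortality 4%), survivor index 0.8, and index 0.5 in the 1% who survive only on losmapimod.
- Survivor mean on losmapimod: (0.95 × 0.8 + 0.01 × 0.5) / 0.96 = 0.765 / 0.96 = 0.797, against 0.800 on placebo, a difference of −0.003.
- With death scored 0: 0.765 − 0.95 × 0.8 = 0.765 − 0.760 = +0.005.

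The sign can therefore reverse, though both figures are small. These steps cover death only. Missed forms and phone follow-up also remove subjects, and the protocol gives nothing from which to size that part.

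**The case against.** **The details may lie in plans not shown.** Section 8.3.1 leaves further populations for health economic data to the RAP, and section 8.3.5.3 leaves the economic evaluations to a separate plan. The absence from the protocol of a rule for missing forms or for valuing death is therefore no fault in itself. That stands. It does not remove the restriction, which section 6.5 writes out as the analysis set.

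**The wording may only name the cohort scheduled for three assessments**, as against two in Part B2. This is possible, but the text speaks of subjects for whom the data points are available, which read literally is a completer rule. If only the cohort is meant, one sentence would settle it.

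**A summary of survivors is a legitimate descriptive question, and section 6.5 announces no test between arms.** Both points are fair. The result then has to be labelled as a result in survivors with complete forms. The arm-bias argument applies only if arms are compared in this set.

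**Stronger readings that the protocol does not support.** A reader might infer that the restriction hides a mortality benefit or harm. It does not: section 6.3.2 lists all-cause mortality as a secondary endpoint with analyses through 4, 12 and 24 weeks, and section 8.3.5.3 plans costs per life year saved and per QALY gained. A reader might also infer that the subset biases the QALY results. Section 6.5 says that the questionnaire supplements the cost-effectiveness work, but nowhere that the three-form subset feeds it.

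**Conclusion.** The point holds as a minor one. Section 6.5 fixes a complete-case set that conditions on survival and attendance to Week 24 and discards partial data. If death counts as loss of health, persistence tends to be overstated. On the assumed survivor index and death rates, the Week 12 to Week 24 fall that the set would miss is about 0.002 to 0.017 index points. The larger 0.0075 to 0.0425 is an overstatement of the Week 24 level and should not be quoted as the error in persistence.

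Any comparison of arms in the subset is unprotected by randomization. Under the assumptions used, the bias is at most about 0.01 index points and its direction cannot be predicted. All these sizes rest on assumed mortality and utility values.

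The subanalysis is exploratory and confined to selected countries within Part B1. The pooled discharge and Week 12 analysis is separate, and no primary or key secondary inference depends on the subset.

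**What to change.** Amend section 6.5 as follows.

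1. Analyse all Part B1 subjects in the EQ-5D countries, using every available form in a repeated-measures model by arm.
2. Report by arm how many subjects have no Week 24 form because of death, and how many because of non-completion.
3. Add a companion analysis of the index, not the VAS, with death scored 0 from the date of death. It should accompany the main analysis and not replace it, because scoring death as 0 mixes mortality with health status and is one debatable choice of estimand.
4. Keep the three-form subset as a supportive display, labelled as applying to survivors with complete forms.

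The cost is a change of wording and slightly more analysis work. No new data are needed, since vital status is already followed to Week 24 (section 4.5).
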